- (5) Protection from Malicious Attack: The TestMyBrain system is implemented as a virtual Linux host, so the primary danger from malware is malicious SQL injection attacks. To guard against this, all entered data are sanitized before being included in any SQL updates.
- (6) Transmission of Data: Participant test data and codes will be transmitted directly from the TestMyBrain.org database to the external researcher using either secure http file transfer or secure SQL connection protocol.
- (7) Storage of Data: Once the study is complete and all data have been downloaded from TestMyBrain.org databases, participant codes that are retained in TestMyBrain databases will be destroyed along with any other study-specific information or information linking a particular testing session with the external research study.

Other Risks:

Information obtained from participants will be treated confidentially. There may be some discomfort associated with nasal spray administration. Nurses at the MGH Clinical Research Center are highly skilled in educating patients about nasal spray use and sensitive to expressions of discomfort. There may also be mild discomfort associated with responding to questions during the diagnostic assessment and answering multiple questionnaires about negative symptoms. Participants will be told that they can refuse to answer any questions that they do not want to answer, and that they can withdraw participation at any point without penalty. Participants with an emergent need for immediate psychiatric care will be referred to the Acute Psychiatry Service at MGH.

VIII. Potential Benefits

Potential Benefits to Participating Individuals:

There are no immediate benefits to the individual for participating in this study. Participants with BDD may receive feedback regarding their symptoms. In the case that participants need referrals for psychiatric treatment, we will facilitate those referrals to MGH or other appropriate facilities. Participants will be provided compensation for their time, in a pro-rated hourly amount of \$15/hour, with a maximum of \$100, plus any additional earnings from the Trust Game (up to \$20), by the end of the study visit for completing all study procedures. In addition, participants will be compensated for parking and public transportation costs such that participants are not responsible for any costs associated with participating in the study.

Potential Benefits to Society:

Data gathered from this study may benefit other individuals with BDD in the future. To date, no studies have examined the oxytocin system in BDD. Given the mounting evidence for oxytocin's role in social and cognitive deficits in autism spectrum disorders, schizophrenia, and other disorders, it is clear that the effects of oxytocin have transdiagnostic implications. Our findings may show that a single administration of intranasal oxytocin may alter social cognitive processes thought to maintain BDD. More importantly, if study aims are achieved, we may learn how to improve treatments for BDD, and identify individuals who would be responsive to oxytocin. Thus, the current study represents a translational approach to investigating potential pathophysiological mechanisms underlying BDD, and will advance knowledge regarding the potential of a promising novel therapeutic agent for BDD.

IX. Monitoring and Quality Assurance

Data and Safety Monitoring Plan:

The study will be monitored for quality assurance and adherence to the protocol according to the following monitoring plan:

A Data Safety and Monitoring Board (DSMB) will be formed consisting of three members who are not associated with the study. The purpose of the DSMB is to: (1) review all adverse events, (2) assess the timeliness, completeness, and quality of the data collected, (3) assess the adherence to protocol requirements, especially measures taken to protect participant safety, and (4) assess the benefit/risk ratio of study procedures. The DSMB will meet once after 40 subjects have been enrolled, and will be provided with the following data prior to this meeting: (1) all adverse events reported, and (2) subject recruitment, enrollment, and dropout numbers. During the meeting, the board will review these data and have 30 days to generate a report, which reflects their opinion of whether the study should be permitted to continue and whether any changes need to be made. This report will then be submitted to the IRB. If any serious adverse events occur during the study, DSMB members will be apprised of them within 24 hours of the event and will be provided unblinded information with regard to the participants' treatment assignment and corresponding study visit. DSMB members will then provide suggestions for the progress of the study, as well as determine whether modifications to the protocol are needed.

Adverse Event Reporting Guidelines:

Definitions:

1. **Adverse event** means any untoward or unfavorable medical occurrence in a human subject, including any abnormal sign (for example, abnormal physical exam or laboratory finding), symptom, or disease, temporally associated with the subject's participation in the research, whether or not considered related to the subject's participation in the research (modified from the definition of adverse events in the 1996 International Conference on Harmonization E-6 Guidelines for Good Clinical Practice).
2. **Serious adverse event** means any event temporally associated with the subject's participation in research that meets any of the following criteria:
 - results in death;
 - is life threatening (places the subject at immediate risk of death from the event as it occurred);
 - requires inpatient hospitalization or prolongation of existing hospitalization;
 - results in a persistent or significant disability/incapacity;
 - results in a congenital anomaly/birth defect; or
 - any other adverse event that, based upon appropriate medical judgment, may jeopardize the subject's health and may require medical or surgical intervention to prevent one of the outcomes listed above (examples of such events include allergic bronchospasm requiring intensive treatment in the emergency room or at home, blood dyscrasias or convulsions that do not result in inpatient hospitalization, or the development of drug dependency or drug abuse).
3. **Unanticipated problem involving risks to subjects or others** means any incident, experience, information, outcome, or other problem that is *unexpected* and related to the research, and that indicates that the research places subjects or others at an increased risk of physical, psychological, economic, legal, or social harm than was previously known or recognized.
4. **Unexpected** means that the incident, experience, or outcome is unexpected (in terms of nature, severity or frequency) given the (a) research procedures that are described in the protocol- related documents, such as the IRB-approved research protocol and informed consent document and (b) the characteristics of the study population being studied.
5. **Unexpected adverse event** means any *adverse event* occurring in one or more subjects participating in a research protocol, the nature, severity, or frequency of which is not consistent with either: (1) the known or foreseeable risk of adverse events associated with the procedures involved in the research that are described in (a) the protocol-related documents, such as the IRB-approved research protocol, any applicable investigator brochure, and the current IRB-

approved informed consent document, and (b) other relevant sources of information, such as product labeling and package inserts; or (2) the expected natural progression of any underlying disease, disorder, or condition of the subject(s) experiencing the adverse event and the subject's predisposing risk factor profile for the adverse event.

Reporting Requirements:

According to the PHRC adverse events reporting policy, PIs are required to report unanticipated problems that occur during the conduct of the study, after study completion, or after subject withdrawal or completion, to be submitted within 5 working days/7 calendar days of the date the PI first becomes aware of the problem. Specifically, reports of unanticipated problems involving risks to subjects or others are to be submitted through Insight/eIRB within 5 working days/7 calendar days of the date the PI first becomes aware of the problem.

Internal adverse events that are **unexpected** and **related/possibly related** to the research and **external** adverse events that are **serious, unexpected and related/possibly related** must be reported to the IRB within 5 working days/7 calendar days of the date the PI first becomes aware of them. Any less serious, expected (e.g., documented in the protocol), or unlikely related adverse events will be reported to the IRB as part of its yearly continuing review process.

Adverse events to be **expected** in the current study, based on Syntocinon® Basic Prescribing Information, previously published data, and from participants in the study to date, include:

- Headaches
- Nausea
- Allergic dermatitis
- Uterine contractions
- Lightheadedness
- Nasal irritation
- Dry mouth/throat
- Feeling of calmness or euphoria
- Anxiety or depression
- Feeling drowsy or sleepy
- Difficulty sitting still
- Trouble concentrating
- Tremors or shakiness

X. References

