We will enroll a maximum of 50 participants to obtain a sample of 40 participants (20 BDD, and 20 healthy volunteers) in the study. Potential participants will be recruited to the MGH OCD and Related Disorders Program through flyers and general clinic advertisements in the General Recruitment Protocol (Protocol #2009P-002227), and databases of research volunteers, such as the Volunteer Research Registry (Protocol #2010P-002496). These referrals are presented in a weekly meeting to the clinicians. In the intake phone call, the coordinator asks the patient if he/she is willing to hear about a research study. If the patient meets initial eligibility criteria (e.g., has BDD) and agrees to be informed about a research study, then our research assistant will call the patient to conduct a BDD-specific phone screen, which has already been approved through the General Recruitment Protocol (Protocol # 2009P-002227). Given our high number of referrals, we do not anticipate any problems recruiting 20 participants with BDD for the current project. In the unlikely event that we have difficulty recruiting, we can collaborate with our colleagues in the Center for Anxiety and Traumatic Stress Disorders Program and Eating Disorders Clinic and Research Program, which receive a number of referrals for BDD. We will never identify potential participants through medical records, and we will never contact potential participants without their permission to be contacted. If a medical colleague identifies one of his or her patients as potentially appropriate for this study, we will request that the colleague encourage the patient to contact a member of the study staff directly. Alternatively, the colleague may ask the patient to give permission to be contacted over the phone by a member of the study staff. Additionally, the OCD and Related Disorders Program has funds available to pay for advertisements if necessary. Our clinic has had recruitment success by posting flyers at mental health private practices, primary care offices, and on the MBTA. Healthy volunteers will be recruited through approved online advertisements through Craigslist and the Partners Clinical Trials website. Healthy subjects will be matched by age and sex, such that group means for age and the number of females will not be significantly different between all 3 study groups.

IV. Subject Enrollment

Methods of Enrollment:

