Prior to analysis, all major variables will be screened for inconsistent or abnormal values, and continuous measures assessed for skewness and outliers. Variable distributions will be examined and transformations made when distributions are skewed or otherwise violate analytic assumptions. Linear regression models will be used, and in all models, the effect of diagnosis will be based not on the global (type III) effect, but on the specific pair-wise comparison of interest: BDD vs. Healthy Controls. Analyses will be conducted using SAS v9.4 (SAS Institute, Cary, NC), and all models will employ a two-sided alpha=0.05 to determine significance.

Aim 1 Analyses:

The primary outcomes will be the Emotion Recognition Task total score and the Trust Game "back transfer" amount. Two sets of outcome scores will be obtained for each subject - one during placebo and the other during oxytocin administration. To test Hypothesis 1a, we will regress placebo outcome scores against diagnosis. To test Hypothesis 1b, we will regress oxytocin outcome scores against diagnosis, and will control for the placebo outcome score. If we find significant differences in oxytocin Emotion Recognition Task total score by diagnosis, we will further examine the 3 Emotion Recognition Task valence categories (positive, negative, neutral) as exploratory outcomes.

Aim 2 Analyses:

Secondary outcomes include the Posner Task difference score for disengagement response latencies between disgust vs. neutral faces, and the Interpretation Questionnaire total score. Mirroring the analyses for the primary aim, we will test Hypothesis 2a by regressing the placebo secondary outcome scores against diagnosis, and will test Hypothesis 2b by regressing the oxytocin secondary outcome scores against diagnosis, controlling for the placebo secondary outcome scores.

Exploratory Analyses:

Exploratory moderators include the BDD-YBOCS total score, YBOCS total score, LSAS total score, BFNE total score, ECR Anxiety subscale mean, ECR Avoidance subscale mean, and IPSM total score. To test the moderation effects, we will enter each moderator (one at a time) into each of the aforementioned linear regression models along with a covariate representing the interaction between the moderator and diagnosis (the term of interest). We will examine moderation of each pair-wise comparison separately.

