For all analyses, we will include concomitant medication use as a covariate, in order to control for the effect of concomitant medications on study results. We will also compare participants who are taking psychotropic medications from participants who are not, on

demographic and clinical variables, to ensure there are no systematic differences between these groups.

Power and Sample Size:

Given the novelty of our approach, no background data on the effects of oxytocin in BDD exist to inform the power calculation. Therefore, the proposed sample size of 40 participants (20 per group) was chosen based on feasibility. With 20 participants per group and a two-sided alpha=0.05, for our primary pair-wise comparison (BDD vs. healthy controls) of the mean within-subject difference (oxytocin vs. placebo) in Emotion Recognition Task total score and Trust Game "back transfer" amount, we will have 81% power to detect a moderate effect size of $f=0.23$.

VII. Risks and Discomforts

Oxytocin-Related Risks and Side Effects:

Between 1990 and 2010, there have been 38 controlled studies involving intranasal delivery of oxytocin (MacDonald et al., 2011). A total of 1,529 participants have received intranasal oxytocin or placebo, and nine studies have included participants (N=182) who had a developmental, medical, or mental health disorder. The dosage of oxytocin has typically been a single dose ranging from 20 international units (IU) to 40 IU. Out of the 1,529 participants who have received intranasal oxytocin or placebo, 279 (18%) reported mild side-effects (MacDonald et al., 2011). The most common side-effect was a feeling of calmness, but this did not differ between those who received oxytocin or placebo. A recent review of studies using intranasal oxytocin supported the short-term use of oxytocin, demonstrating that oxytocin produced minimal side-effects, no detectable differences in side-effects between oxytocin or placebo recipients, no subjective changes in recipients, and is equally safe to use with vulnerable populations as with healthy adults (MacDonald et al., 2011). The proposed study intends to use a single 24 IU dose of intranasal oxytocin, which has been the most commonly used dose in previous trials (25 out of 38 studies).

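### Age and sex matching is judged only by non-significance at 20 per group and neither variable is in any model, so an imbalance that passes could shift the BDD v control contrast

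*Combined protocol and SAP*

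**What the plan says.** - **Matching.** Section III (Source of Subjects and Recruitment Methods) says "Healthy subjects will be matched by age and sex". It describes the intended result as "group means for age and the number of females will not be significantly different between all 3 study groups". It gives no matching procedure, tolerance, test or significance level for this. The same section plans 20 BDD and 20 control participants, which is two groups.
- **Models.** Section VI (Aim 1 Analyses): "To test Hypothesis 1a, we will regress placebo outcome scores against diagnosis". For Hypothesis 1b, "we will regress oxytocin outcome scores against diagnosis, and will control for the placebo outcome score". Aim 2 repeats both forms for the secondary outcomes. Concomitant medication use is a covariate throughout, and the exploratory models add one moderator and its interaction with diagnosis. Age and sex are in none of these models.
- **Randomisation.** Section IV (Treatment Assignment Procedures) randomises spray order only.
- **Planned check.** The one demographic comparison in Section VI is between participants who do and do not take psychotropic medication, not between BDD and controls.
- **Eligibility and sources.** Section III admits adults from 18 with no upper age limit. BDD participants are treatment-seeking and come largely through clinic referral. Controls come from online advertising.

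**The concern.** A non-significant difference between two groups of 20 is weak evidence that they are alike. If a sizeable age or sex difference passes, and the variable is related to the score, part of that difference goes into the diagnosis coefficient.

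Hypotheses 1a and 2a are plain between-group comparisons of placebo scores, so the crossover gives them no protection. Hypotheses 1b and 2b adjust for the participant's own placebo score, which removes part of an effect of age on the level of the score. It would not remove an effect of age or sex on the response to oxytocin.

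At stake is whether a reported BDD deficit, or a different oxytocin response in BDD, might partly be an age or sex difference. The plan names no analysis by diagnosis that would show this.

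**Working it through.** **Inputs from the protocol:** 20 per group; two-sided 0.05, stated for the outcome models ("all models will employ a two-sided alpha=0.05 to determine significance") and assumed here for the balance check; 81% power at f=0.23. **Assumptions, not in the protocol:** age-score correlation r of 0.3 (range 0.2-0.5), test-retest correlation ρ of 0.5, and any age SD in years.

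**1. The plan's power figure.** For a two-group by two-measure interaction, λ = f²·N·m/(1−ρ) = 0.0529 × 40 × 2 / 0.5 = 8.464. With 1 and 38 df, power is 80.9%, which matches the stated 81%. It needs ρ=0.5: power is 66.9% at ρ=0.3 and 95.5% at ρ=0.7.

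**2. What passes for age.** The largest non-significant gap is t(0.975, 38) × √(2/20) = 2.024 × 0.316 = 0.640 SD. That is 5.1, 6.4 or 7.7 years if the age SD is 8, 10 or 12. A true gap of 0.5 SD is non-significant 66% of the time.

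**3. What passes for sex.** The answer depends on the test, which the plan does not name.

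| Women, of 20 v 20 | Fisher p | Uncorrected chi-square p |
|---|---|---|
| 8 v 15 | 0.054 (passes) | 0.025 (fails) |
| 7 v 13 | 0.113 (passes) | 0.058 (passes) |

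Power to detect 50% v 70% women is 25%.

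**4. Hypothesis 1a at the limiting age gap.** Shift = r × gap: 0.2 × 0.64 = 0.13, 0.3 × 0.64 = 0.19 and 0.5 × 0.64 = 0.32 SD. Simulated with no diagnosis effect and the observed gap held at 0.64 SD, the false-positive rate is about 6%, 8% and 13%. At r=0.1 and a gap of 0.63 SD it is 5.6%.

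**5. Hypothesis 1b.** At a gap of 0.63 SD and ρ=0.5, with age affecting only the level of the score, the shift is about 0.10 SD and the error rate 5.7% at r=0.3. At r=0.5 they are 0.15 SD and 7.4%.

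**6. Typical rather than limiting cases, Hypothesis 1a.** With no population age gap, and samples kept only if the age test is non-significant, the error rate is 5.0%, 4.8% and 4.3% at r=0.2, 0.3 and 0.5. With a systematic 0.5 SD gap, the rate among accepted samples is 5.2%, 5.4% and 6.2%.

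**7. Effect of adjustment.** With age in the model, the simulated shift returns to within 0.01 SD of zero and the error rate to 4.6-5.5%.

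**8. Power after adding both covariates** (36 df, λ from step 1):

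- Well matched, allowing a variance factor of 1.054 for chance correlation with diagnosis: 8.464/1.054 = 8.03, so about 79% if the covariates explain nothing. If they explain 10% of variance, 8.03/0.90 = 8.92, so about 83%.
- At the worst passing limits, the variance factor is 1 + 10 × 0.64²/38 = 1.11 for age. For 8 v 15 women it is 1 + 10 × 0.35²/8.55 = 1.14, where 8.55 is the within-group sum of squares. For both, if uncorrelated within groups, it is about 1.25. Then 8.464/1.25 = 6.77, so about 72% if the covariates explain nothing.

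Like the plan's own figure, step 8 leaves out the degrees of freedom for the medication and placebo-score terms.

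**The case against.** The protocol does intend to match, and the non-significance clause describes the result of that matching. If matching works, the remaining differences are due to chance, and the standard error already allows for them: step 6 shows no inflation. The larger error rates need both a matching failure and a draw close to the pass limit. The age-score correlation is assumed, and at 0.1 the effect is negligible. Matching without adjustment is also a defensible choice in a small laboratory comparison. All of this stands, and it limits the size of the point. It does not remove the omission, because the stated criterion does not ensure that matching has worked.

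Two stronger readings are tempting, and the protocol supports neither.

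- **Higher error rates.** A reader might treat 0.64 SD as a population gap and infer an error rate of about 9% (7-17%). But 0.64 SD is the largest *observed* gap that passes. Holding it there gives 6-13%, and accepted samples from a population with a 0.5 SD gap give about 5-6%.
- **Sex and oxytocin response.** Every woman must use a low-dose hormonal contraceptive, so a sex imbalance is also an imbalance in contraceptive use. A reader might infer that this biases Hypothesis 1b. The protocol gives no figure for an effect of sex or contraceptive use on oxytocin response, and the contraceptive rule is the same in both groups. It is a reason to include sex as a covariate, not evidence of bias.

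**Conclusion.** The point holds as a modest, conditional weakness. The balance standard is a non-significant test with low power, and no model contains age or sex, although diagnosis is not randomised.

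Hypothesis 1a is the most exposed of the primary hypotheses, and 2a has the same form. In the limiting case that still passes, the Hypothesis 1a contrast shifts by 0.19 SD (0.13-0.32) and the false-positive rate is about 8% (6-13%). This rests on an assumed age-score correlation of 0.3 (0.2-0.5). Hypothesis 1b is affected less, at about 5.7% for r=0.3 and ρ=0.5, provided age acts on the level of the score and not on the response to the drug. With successful matching there is no inflation. The plan therefore allows this bias but does not make it likely, and the case for change is that the protection is cheap.

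The reference to three groups conflicts with the two-group design and needs correcting in any case.

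**What to change.** - **Section VI:** pre-specify age and sex as covariates in the models for Hypotheses 1a, 1b, 2a and 2b, alongside concomitant medication use.
- **Section III:** change the reference to three study groups to two.
- **Optional, Section III:** judge balance by the size of the age and sex differences as controls are recruited, in place of a significance test, with a tolerance chosen by the sponsor.

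The cost is a sentence in each section and two degrees of freedom. No new data are needed, because both variables are required for the matching. On the plan's power basis (ρ=0.5 assumed), power moves from 81% to about 79% if the groups are well matched and the covariates explain nothing, and to about 83% if they explain 10% of variance. It falls to about 72% if the groups sit at the worst passing limits and the covariates explain nothing. That last figure is a reason to match closely as well as adjust.

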An advanced doctoral student or a doctoral level member of the study staff will obtain written informed consent, and will thoroughly review the consent form with the potential participant. If an advanced doctoral student obtains consent, a licensed physician investigator will be available to speak with the subject during the consent process. Subjects who are consented by advanced doctoral students will be offered the option of speaking with a physician Investigator during the consent process and this will be recorded in research records. During the consenting process, potential participants will be apprised of the voluntary nature of their participation in the study and that they can withdraw at any point in the study without penalty. Specifically, we will reassure all potential participants that refusal to participate will in no way influence their care or affiliation with the Clinics at the Massachusetts General Hospital or any other Harvard Medical School affiliated hospital. Potential participants will be informed that the study will examine how oxytocin impacts their performance on different social cognitive tasks, but they will not be informed as to the exact study hypotheses (e.g., how oxytocin's effects on social and cognitive functioning may relate to their BDD symptoms). It will be necessary to use incomplete disclosure at the outset of the study to ensure maximum internal validity of study results. Potential participants will also be given as much time as needed to consider participation, and will be given an opportunity to ask questions about the study prior to signing the consent form. We will obtain written informed signed consent through the use of a PHRC approved written consent from all participants before they enter into the study and start study procedures. After signing the consent form, participants will be given a copy of the consent, and the original copy will be filed in a locked file separate from study data in a research office.

[figure not shown]
Treatment Assignment Procedures:

Given the cross-over design, all participants will receive an oxytocin and placebo nasal spray at two separate visits. The MGH Research Pharmacy will randomize the order of nasal sprays that will be given to participants, and will thus be un-blinded of assigned drug condition for participants' study visits. All other study staff, as well as participants themselves, will be blind to drug condition.

V. Study Procedures

Overview of Study Procedure:

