The study will consist of 3 study visits in total. The first visit will involve the diagnostic assessment and medical screen to determine eligibility for the study, in addition to the administration of clinician-administered and self-report questionnaires. This visit will take approximately 2.5 hours to complete. If participants are eligible, they will be asked to return to the clinic for two additional study visits, which will be identical in procedure and take approximately 2 hours each to complete. Female participants must complete Visits 2 and 3 during the active phase of their contraceptive medication (e.g. not during their menses); female subjects using multiphasic contraceptives must be on the same dose of ethinyl estradiol for both Visit 2 and 3. Participants will be instructed to avoid alcohol, caffeine, and nicotine for 24 hours prior to Visits 2 and 3. These visits will involve the administration of both an oxytocin and placebo nasal spray, in randomized order, and the completion of various social cognition tasks. They will be separated by a one-week washout period (**maximum 28 day** window period). The study design and procedures are represented in the following schematic:

[figure not shown]
Diagnostic Assessment and Medical Screen:

After obtaining informed consent, participants will be administered the Structured Clinical Interview for DSM-IV (SCID-I/P; First, Spitzer, Gibbon, & Williams, 2002) to determine diagnostic eligibility. The SCID allows the investigator to assess all diagnostic inclusion and exclusion criteria. Participants who are recruited for the healthy control

group will be given the SCID-I/P to confirm the absence of Axis I psychopathology. Participants who meet the diagnostic inclusion and exclusion criteria will be given a medical screen consisting of a history and physical examination (H&P) by a study nurse or physician to determine the participant's eligibility and safety for the study. In addition, a urine pregnancy test will be given to females during this visit, as well as at the beginning of Visits 2 and 3 to ensure continued eligibility.

Investigational Agent (dose, method, schedule of administration, dose modifications):

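### No balancing of spray order within the BDD and control groups is specified, and the planned regressions have no order term, so a visit effect can enter the diagnosis contrast by chance

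*Combined protocol and SAP*

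**What the plan says.** Section IV, Treatment Assignment Procedures: "The MGH Research Pharmacy will randomize the order of nasal sprays that will be given to participants". Section V, Overview of Study Procedure, adds only that the two dosing visits involve "administration of both an oxytocin and placebo nasal spray, in randomized order". Neither section gives an allocation ratio, a block size or strata. By contrast, section V (Tasks) states that the order of the tasks is counterbalanced across participants.

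Section VI, Aim 1 Analyses: "To test Hypothesis 1a, we will regress placebo outcome scores against diagnosis". For Hypothesis 1b the oxytocin score is regressed on diagnosis with the placebo score as covariate. The Aim 2 models mirror these two. The only further covariate is concomitant medication use. No model has a term for visit, period or sequence.

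Power and Sample Size: "With 20 participants per group and a two-sided alpha=0.05", the plan claims 81% power at f = 0.23 for the BDD v control comparison "of the mean within-subject difference (oxytocin vs. placebo) in Emotion Recognition Task total score" and in the Trust Game amount.

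**The concern.** In an ordinary crossover the drug contrast is within person, and randomised order guards it against visit effects. Here the contrast of interest is between two diagnostic groups. A visit effect cancels from it only if the same share of each group receives oxytocin first, or if the model adjusts for order. The plan specifies neither.

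A visit effect is plausible. The two dosing visits follow the same procedure, and the protocol mentions no alternate forms of the emotion recognition task, the interpretation questionnaire or the Posner task. Participants also meet the Trust Game again at the second dosing visit. The documents do not give the size or direction of any such change.

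At stake is the reading of one small trial. If, say, 8 of 20 BDD participants and 12 of 20 controls happen to receive oxytocin first, part of the estimated difference in oxytocin response is practice or familiarity. Hypotheses 1a and 2a are exposed too, because the placebo scores they use come from different visits in different proportions in the two groups.

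**Working it through.** **Inputs from the documents.** 20 BDD and 20 controls; two-sided alpha 0.05; f = 0.23; stated power 81%; models as above.

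**Assumptions, not in the documents.** Within-person correlation ρ = 0.5; visit effect δ (Visit 3 minus Visit 2) of 0.25, 0.5 or 0.8 SD of the score, equal in both groups; normal scores; medication covariate omitted.

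**1. The plan's own figure.** For a group-by-condition interaction with N = 40 and m = 2 measurements, λ = f²·N·m/(1−ρ) = 0.0529 × 40 × 2 / 0.5 = 8.464. The noncentral F(1, 38) then gives power 0.809, which agrees with 81%. The match depends on ρ: power is 0.518 at ρ = 0 and 0.955 at ρ = 0.7. At ρ = 0.5 the effect powered for is 2√(8.464/40) = 0.92 SD of the difference score, and that SD equals the score SD because √(2(1−0.5)) = 1. This serves as the yardstick below.

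**2. Chance of imbalance.** Let X and Y be the oxytocin-first counts in the two groups.

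| Scheme | P(counts differ by ≥ 4) | P(counts differ by ≥ 6) |
|---|---|---|
| Simple 1:1 | 26.8% | 8.1% |
| 20:20 overall, ignoring diagnosis | 34.3% | 11.3% |
| Blocks of 4, ignoring diagnosis | 34.6% | 11.3% |

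The first row is exact: X − Y + 20 is Bin(40, 0.5), so P(|X−Y| ≥ 4) = 2·P(Bin(40, 0.5) ≤ 16) = 0.268. The second is hypergeometric and the third simulated. With an exact 20:20 list the difference can only be even, which raises these tail figures; the mean absolute difference is 2.5 in both of the first two rows. Balancing order overall therefore does not balance it between the diagnoses.

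**3. Leakage.** Let p_B and p_C be the oxytocin-first shares. Oxytocin-first participants take placebo at Visit 3, so δ adds to their placebo score; for the others it adds to the oxytocin score. In absolute size:

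- Hypothesis 1a contrast: δ·|p_B − p_C|.
- Hypothesis 1b contrast: (1 + b)·δ·|p_B − p_C|, where b is the fitted placebo-score slope.

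The visit effect itself lowers the slope: b ≈ (ρ − q)/(1 + q), with q = p(1−p)δ². For 8 v 12 and δ = 0.5, q = 0.24 × 0.25 = 0.06, b = 0.44/1.06 = 0.415, and the shift is 1.415 × 0.5 × 0.2 = 0.14 SD. Simulating the planned 1b regression gives the same answer.

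| Split | Contrast | δ = 0.25 | δ = 0.5 | δ = 0.8 |
|---|---|---|---|---|
| 8 v 12 | 1b | 0.07 | 0.14 | 0.21 |
| 8 v 12 | 1a | 0.05 | 0.10 | 0.16 |
| 7 v 13 | 1b | 0.11 | 0.21 | 0.31 |
| 7 v 13 | 1a | 0.075 | 0.15 | 0.24 |

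At δ = 0.5, the 1b shifts are 0.14/0.92 = 15% and 0.21/0.92 = 23% of the effect powered for.

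**4. Behaviour of the 1b test under the null** (simulated, ρ = 0.5).

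| Allocation and model | Rejection rate at δ = 0.25 / 0.5 / 0.8 |
|---|---|
| 8 v 12, no order term | about 5 to 6% throughout |
| 7 v 13, no order term | 6.4% / 8.8% / 12.2% |
| Simple randomisation, no order term, averaged | 4.7% / 5.0% / 5.1% |
| 10:10 in each group, no order term | 4.6% / about 3.5% / 2.4% |
| Any of these with an order term | about 5% throughout |

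Averaged over simple randomisations, the bias is about zero. The SD of the estimate without an order term is 0.28 / 0.30 / 0.33. With an order term it is 0.28 throughout. With 10:10 balance and no order term it is 0.28 / 0.28 / 0.29.

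**The case against.** The strongest reply is that the protocol leaves the method to the pharmacy, which may already block or stratify, and that the study schematics are not shown in the text available. This stands in part. A reader might infer that order is known to be unbalanced by diagnosis; the documents support only that no such balancing is specified.

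A reader might also infer that false positives are inflated overall. They are not: randomisation keeps average bias near zero and average type I error near 5%. Even given an 8 v 12 split, rejection rises little, because the visit effect also enlarges the residual. It rises clearly only for rarer splits such as 7 v 13.

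A leakage of 2·δ·|p_B − p_C| is tempting as well. That is right for a simple oxytocin-minus-placebo change score, where 8 v 12 at δ = 0.5 would give 0.2 SD. The planned 1b model adjusts for the placebo score, so the figure there is 0.14 SD.

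Finally, this could be read as an allocation flaw independent of the models. It is not, since an order term removes the shift whatever the split. With that term, balancing adds little precision: the SD was about 0.28 under both simple randomisation and exact balance at δ = 0.5. What remains is that the plan has neither safeguard. And if δ is near zero, the problem disappears.

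**Conclusion.** The point holds in a limited form. The plan specifies no balance of spray order by diagnosis and no adjustment for it, although its primary and secondary tests are between diagnoses. If the order is randomised without strata, there is roughly a 27 to 35% chance of a between-group difference of 4 or more in oxytocin-first counts, and 8 to 11% of 6 or more.

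The consequence is chance bias conditional on the split drawn. For Hypothesis 1b it is 0.07 to 0.21 SD at 8 v 12 and 0.11 to 0.31 SD at 7 v 13, with a modest loss of precision on average. These sizes rest on an assumed correlation of 0.5 and assumed visit effects of 0.25 to 0.8 SD. This is not systematic bias. It is worth correcting because the trial is small, is run once, and can be protected at almost no cost.

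**What to change.** 1. State in Treatment Assignment Procedures that spray order is randomised 1:1 in permuted blocks, stratified by diagnosis: one pharmacy list for BDD and one for controls. Have the diagnosis group written on each prescription so that the pharmacy can use the right list.
2. Add spray order (visit sequence) as a covariate in the Hypothesis 1a, 1b, 2a and 2b models.

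Both parts are needed. Balancing alone removes the shift but leaves visit variation in the residual, so the 1b test becomes conservative. The order term alone removes the shift, but stratified lists keep the comparison balanced by design.

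The cost is a second pharmacy list, a few sentences of protocol text and one degree of freedom per model. Blocks make the last assignments in each block slightly predictable, but only the pharmacy sees the list.
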